1. STUDY OBJECTIVES

1.1 Primary Objective

The primary objective is to examine the degree to which MT and SMT exert effects on the non-specific mechanism, EO function. We will test to what degree MT and SMT produce pre- to mid- to post-treatment changes in EO function. Hypothesis 1: MT and SMT will produce near equivalent effects on EO function.

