Interested individuals will be able to contact the designated study research assistant by phone or email. Individuals expressing an interest will first be provided verbally with information on the study procedures, risks, and benefits, and if interested, will be given the opportunity to read the IRB-approved informed consent form. All questions from potential subjects will be answered by the study representative as accurately as possible. All individuals agreeing to participate will provide written informed consent prior to beginning any study procedures. Subject recruitment and consent procedures will be carried out by individuals designated and trained by each site PI and the IRB to carry out these procedures (i.e., the proposed research assistants). Potential subjects will be told that they will be compensated \$605 for their time and effort to participate in all of the assessment and therapy sessions. In the Consent Form, it will be emphasized that subjects may discontinue participating at any time and still receive prorated compensation. The recruiter will inform potential subjects that participation is completely voluntary, and they may withdraw at any time without penalty or running the risk of jeopardizing current and future treatment at the Rush or Vanderbilt medical centers.

Study patients (n=286) will be randomized to receive either MT or SMT. The order of drug administration for each laboratory session will also be separately randomized and counterbalanced (placebo vs. naloxone) for both of the assessment time points (in double-blinded fashion). All randomization will be carried out using the Proc Plan procedure in SAS version 9.2 (SAS Institute, Cary, NC). This SAS procedure will be used to generate a randomization schedule for each sequential study slot (MT vs. SMT and the order of naloxone/placebo administration in each set of lab visits). Study subjects will be assigned to these previously randomized study slots in the order that they are enrolled, and the previously determined randomization status associated with each slot will determine the intervention condition each subject is in and the order of drug administration for each session. This randomized order will be maintained even if study appointments are missed (applies only to drug order in laboratory sessions). In the event of a true study dropout, that slot is considered used and future subjects will not be assigned to that slot.

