9.2 Sample Size and Randomization

Power consideration for Aim 1:

Based on past findings, we expect that Mindfulness Training (MT) and Spinal Manipulation Therapy (SMT) will have near-equivalent effects on the primary outcome, changes in EO function. We ran power calculations assuming a true difference of 0 between MT and SMT. Please note that we plan to enroll 286 participants to achieve a sample size of 240 completed participants. See below:

Power Analysis of Two-Sample T-Test for Testing Equivalence Using Differences

Power	MT	SMT	Lower	Upper	True Difference	Standard Deviation	Alpha	Beta
	Group	Group						
	Sample Size (N1)	Sample Size (N2)	Lower	Upper	True Difference	Standard Deviation	Alpha	Beta
0.851	120	120	-3.0	3.0	0.0	7.5	0.050	0.149
0.950	120	120	-3.5	3.5	0.0	7.5	0.050	0.050
0.987	120	120	-4.0	4.0	0.0	7.5	0.050	0.013

An equivalence test of means using two one-sided tests on data from a parallel-group design with sample sizes of 120 in the reference group and 120 in the treatment group achieves 85% power at a 5% significance level when the true difference between the means is 0.0, the standard deviation is 7.5, and the equivalence limits are -3.0 and 3.

Power considerations for Aim 2:

We will test effects of MT and SMT on the treatment-specific mechanisms, pre-post treatment changes in mindfulness and spinal stiffness. Per reviewer suggestions and input from our co-I, [name], we expanded the assessment of “mindfulness” to include pain unpleasantness/bothersome ratings and the Multidimensional Assessment of Interoceptive Awareness (MAIA) scale as well as the Five Facets of Mindfulness Questionnaire (FFMQ). We expect MT to produce larger changes in the mindfulness measures than SMT, and for SMT to produce larger changes in spinal stiffness than MT.

Null Hypothesis: Mean1=Mean2. Alternative Hypothesis: Mean1 \neq Mean2

Allocation

Power	N1	N2	Ratio	Alpha	Beta	Mean1	Mean2	S1	S2
0.800	120	120	1.0	0.050	0.200	0.36	0.00	1.00	1.00
0.983	120	120	1.0	0.050	0.017	0.53	0.00	1.00	1.00

Treatment group sample sizes of 120 and 120 will achieve 80% power to detect a difference of Cohen's $d = 0.36$. With a larger effect – $d = .53$ -- at $\alpha=0.05$ we will have 98.3% power to detect a treatment difference.

Power considerations for Aim 3:

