9.5.1 Primary Outcome

Our primary mechanism outcome is pre- to post treatment changes in EO function.

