9.6 Data Analyses

Primary analyses will be conducted on an ITT basis.

Aim 1: To determine the degree to which MT and SMT produce effects in nonspecific mechanisms.

The primary analyses will employ the two-sample t-test to compare mean change in each nonspecific mechanism within a noninferiority test construct to compare mean change in outcome from pre to post treatment between the two treatment arms. An overall, 2-sided, significance level of 0.05 will be used. Linear mixed models will be used as a supplemental analysis, allowing us to utilize all data collected, account for within subject variation, and model changes over time. The fixed effect part of the model will be

$Mechanism_{ij} = \beta_0 + \beta_1 Time_{ij} + \beta_2 Tx_i + \beta_3 (Tx_i * Time_{ij}) + \varepsilon_{ij}$ for subject i at visit j.

If β_3 is significantly negative ($p < .05$), this would indicate that the mechanism variable decreased more in SMT than in MT (Fitzmaurice, Laird, & Ware, 2011). In case of a significant interaction, we will test simple slopes of Time for each Treatment Condition separately AND by testing post treatment differences between MT and SMT controlling for pre-treatment values.

Candidate covariance structures will be assessed using the data's correlation structure and Akaike's Information Criterion (AIC). Random coefficients (e.g. random intercept and/or random slope) will be included in the model if they significantly improve the model fit as determined by the likelihood ratio test. Standardized residuals and Cook's distance will be used to assess the influence of outliers and individual observations. Residual plots will be used to check the multivariate normal distribution assumption. The pattern of missing data will be examined to determine its missing mechanism and the amount. If data are missing not at random (MNAR), data imputations may be used. If other deviations from the model assumptions are detected, appropriate measures will be taken to prevent inferential bias, e.g. data transformations and use of bootstrap techniques to compute standard errors.

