In the absence of interactions, we will use linear mixed effects regression models to test the degree to which changes in non-specific and specific mechanisms account for unique and shared variance in pre-post outcome changes. More specifically, 0-order correlations among mechanism and outcome pre-post change scores will reveal “candidate” mechanisms (i.e., those with significant associations with pre-post outcome changes). We will use a series of hierarchical regressions to examine the degree to which ostensibly different mechanisms account for shared or unique variance in outcome changes. Such analyses will allow us to identify common areas of mechanism overlap (e.g., changes in self-efficacy and pain catastrophizing accounting for much shared variance in pain changes), and mechanism uniqueness (e.g., changes in spinal stiffness accounting for significant unique variance in pain changes even with other mechanism changes controlled).

Aim 4: Address competing causation pathways.

First, we will use an approach and techniques that we have used in previous publications [eg, [name], J.W., Nielson, W.R., Jensen, M.P., Heapy, A., Czlapinski, R., & Kerns, R.D. (2015). Specific and general therapeutic mechanisms in cognitive-behavioral treatment of chronic pain. *Journal of Consulting and Clinical Psychology*. 83, 1-11. PMID: 24979313]. Namely, we will test lagged and cross-

lagged effects using pre- to mid-treatment and mid- to post-treatment epochs. Given that endogenous opioid functioning will be assessed only at pre-and post-treatment, and given that the working alliance and subject expectations for benefit will be assessed only at 3- and 6-weeks, this approach will allow to examine comparable effects across all our specific and non-specific mechanisms. Residual change scores for all mechanism and outcome variables will be computed by regressing mid-treatment on pre-treatment values (i.e., a pre-mid residual change score), and regressing post-treatment on mid-treatment values (i.e., mid-post residual change score). For lagged relationships, regressions will be performed to identify the unique effect of pre-mid mechanism changes on mid-post outcome changes. This will require statistically controlling for the path from pre-mid mechanism change to mid-post mechanism change and pre-mid outcome change to mid-post outcome change. See Figure 1 and 2 below. The red line is the target lagged effect. The two blue lines are the paths to be controlled.

Figure 1

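### The primary endogenous opioid (EO) comparison is an unadjusted t-test on change. It is valid, but it gives up precision that the pre-treatment EO value, already collected, would supply

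*Protocol*

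**What the plan says.** - **Outcome** (Section 9.5.1): "Our primary mechanism outcome is pre- to post treatment changes in EO function".
- **Primary analysis** (Section 9.6, Aim 1): a "two-sample t-test to compare mean change in each nonspecific mechanism", framed as a noninferiority test. No covariate enters this test.
- **Power** (Section 9.2): two one-sided tests at 5% with 120 per arm and a true difference of 0; "the standard deviation is 7.5, and the equivalence limits are -3.0 and 3". Stated power is 0.851.
- **Hypothesis** (Section 1.1): "MT and SMT will produce near equivalent effects on EO function".
- **Baseline adjustment** (Section 9.6): it appears only as "testing post treatment differences between MT and SMT controlling for pre-treatment values", a follow-up step after a significant treatment-by-time interaction in the supplemental mixed model.
- **Measurement times** (Section 9.6, Aim 4): "endogenous opioid functioning will be assessed only at pre-and post-treatment".
- **Candidate covariates** (Section 9.6): site, age and baseline variables that differ between arms at p < .20, chosen by LASSO. Pre-treatment EO is not named.

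**The concern.** A two-sample t-test on change is a regression of the post-treatment value on arm and baseline, with the baseline slope forced to 1. Unless the true slope is 1, estimating it leaves less residual variance and a narrower interval for the same arm difference. This matters more than usual here because the primary claim is equivalence. Under Section 9.2 the 90% confidence interval must lie wholly inside ±3, so a needlessly wide interval raises the chance that two truly equivalent treatments are not shown to be so.

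The other planned analyses do not make this good:

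- The step that controls for pre-treatment values needs a significant interaction, which is the opposite of what the hypothesis expects.
- The supplemental mixed model has a free treatment term at baseline and, for EO, only two time points. With complete pairs its interaction coefficient is the unadjusted difference in mean change.
- Pre-treatment EO could enter through the LASSO list only if it happened to differ between arms, and that list does not apply to the t-test.

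**Working it through.** **Inputs from the protocol.** 120 completers per arm, SD 7.5, limits ±3, true difference 0, 5% per side (Section 9.2); 286 enrolled (Section 9.2).

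**Assumptions, not in the protocol.** 7.5 is the SD of EO change. ρ is the pre-post correlation of EO, taken as 0.3 to 0.9. k is the post/pre SD ratio, taken as 1 and then varied.

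**1. The protocol's own figure.** Exact power of the two one-sided tests, integrating over the sampling distribution of the residual SD with 238 df, is 0.8515, 0.950 and 0.987 at limits ±3, ±3.5 and ±4. The protocol states 0.851, 0.950 and 0.987. The SE is 7.5 × √(2/120) = 0.968, and the 90% half-width is 1.651 × 0.968 = 1.60.

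**2. Effect of estimating the slope.** With pre-treatment SD s:

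- Variance of change = s²(1 + k² − 2ρk).
- Residual variance given baseline = k²s²(1 − ρ²).
- With k = 1 the ratio is (1 − ρ²) / [2(1 − ρ)] = (1 + ρ)/2, so the adjusted SD is 7.5 × √[(1 + ρ)/2].

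**3. Allowing for the covariates.** Baseline and site leave 236 df. Their chance imbalance inflates the variance by 1 + 2/235, about 0.9%.

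| ρ | Adjusted SD | Power, baseline only | Power, baseline + site | 90% half-width, baseline + site | n per arm for 0.851 |
|---|---|---|---|---|---|
| unadjusted | 7.50 | – | 0.851 | 1.60 | 120 |
| 0.3 | 6.05 | 0.971 | 0.970 | 1.29 | 80 |
| 0.5 | 6.50 | 0.945 | 0.944 | 1.39 | 92 |
| 0.7 | 6.91 | 0.912 | 0.909 | 1.48 | 104 |
| 0.9 | 7.31 | 0.873 | 0.869 | 1.57 | 115 |

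(The first row is the planned t-test, with no covariates.)

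Simulation of the baseline + site model, 8,000 trials per setting, gave 0.969, 0.946, 0.910 and 0.878, against 0.855 to 0.858 for the t-test. Type I error at a true difference of 3 was 0.051 to 0.053 for all models (checked at ρ 0.5 and 0.9).

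**4. Fewer completers.** With 110 per arm, power is 0.811 unadjusted against 0.955, 0.921, 0.878 or 0.831 adjusted.

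**5. Unequal SDs.** The true slope is ρk. Over the same four ρ values, adjusted power is 0.975 to 0.993 at k = 0.8 and about 0.86 to 0.93 at k = 1.25. At ρ = 0.8 and k = 1.25 the slope is exactly 1. There is then nothing to gain, and adjusted power is 0.848.

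**6. If 7.5 is the SD of a single-time EO score.** The SD of change is 7.5 × √[2(1 − ρ)] and the adjusted SD is 7.5 × √(1 − ρ²). Power on change is 0.666, 0.851, 0.981 and above 0.999 at ρ 0.3, 0.5, 0.7 and 0.9. With baseline adjustment it is 0.889, 0.945, 0.993 and above 0.999.

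**7. The supplemental model.** On one simulated complete data set (ρ = 0.5), the mixed-model interaction was −1.0637 (SE 0.903). The difference in mean change was identical, and the baseline-adjusted SE was 0.802.

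**The case against.** **No error, only a preference.** The t-test is valid, its power reproduces, and Sections 9.2, 9.5.1 and 9.6 agree on an unadjusted comparison of change. Covariates are often settled in a SAP. This stands as far as validity goes. But the protocol itself names the t-test as primary, so the choice is already fixed here.

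**Unknown size.** The gain depends on ρ, on k and on what 7.5 measures. Across the cases above it runs from about +0.14 (k = 0.8, ρ = 0.3) to −0.003 (slope 1). This stands, and it is why only ranges are given. The downside is very small compared with the upside.

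**Equivalence or noninferiority.** Every power figure here assumes Section 9.2's two one-sided tests at 5% each, whereas Section 9.6 speaks of noninferiority and a two-sided 0.05 level. That conflict is a separate point, but the magnitudes do depend on how it is settled. At 2.5% per side, planned power is 0.740 and adjusted power is 0.936, 0.888, 0.830 or 0.767. The gain remains.

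**The mixed model recovers something when post values are missing.** Suppose all 143 per arm (286/2) have pre-treatment EO and 120 have post. Likelihood estimation then recovers at most 1 − 120/143 = 16% of the variance gap, giving power of about 0.869 at ρ = 0.5 against 0.944 adjusted. This is correct but small, and it applies only to a supplemental analysis.

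**Conclusion.** The concern holds, as a matter of efficiency and not of bias. Under Section 9.2's test, with 7.5 as the SD of change and equal pre and post SDs, baseline adjustment with site raises power by 0.02 (ρ = 0.9) to 0.12 (ρ = 0.3). The risk of missing true equivalence falls from 15% to between 13% and 3%. With equal SDs the adjusted analysis falls below 0.851 only when ρ exceeds about 0.98, and then reaches no lower than 0.848. The direction is the same if 7.5 is a single-time SD or if 2.5% per side is used. The exact gain cannot be fixed from the protocol, because it gives neither ρ nor the SD ratio and does not say what 7.5 measures.

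**What to change.** In Section 9.6, make the primary EO analysis a linear regression of post-treatment EO on arm, pre-treatment EO and site, fitted whatever the baseline balance. Compare the 90% confidence interval for the arm coefficient with ±3, as in Section 9.2, and keep the t-test on change as a sensitivity analysis. State in Section 9.2 whether 7.5 is the SD of change. The same form, without the ±3 margin, suits other Aim 1 and Aim 2 mechanisms that have both a baseline and a post-treatment value.

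Drug order "will also be separately randomized and counterbalanced (placebo vs. naloxone) for both of the assessment time points" (Section 4.3), so order indicators for the two time points could be added. They help only if there is a first-day/second-day effect, whose size the protocol does not give, and no gain is claimed for them. With no such effect, power with all four covariates would be 0.969, 0.942, 0.907 or 0.866 at the four ρ values.

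The cost is small. Pre-treatment EO and site are already recorded, and allowing for chance imbalance of baseline and site lowers adjusted power by only 0.001 to 0.003. The change does alter the named primary analysis, so it needs a protocol modification reviewed by both IRBs (Section 11.1). It should be dated before any EO results are seen by arm.

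### Section 9.6 prescribes a noninferiority test at 2-sided 0.05 for the primary outcome, although the hypothesis is near-equivalence and the 85% power belongs to two one-sided equivalence tests

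*Protocol*

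**What the plan says.** Section 9.5.1 fixes the primary outcome: "Our primary mechanism outcome is pre- to post treatment changes in EO function". Section 1.1 gives the hypothesis for it: "Hypothesis 1: MT and SMT will produce near equivalent effects on EO function". That hypothesis has no direction.

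Section 9.2 sizes the trial for this outcome with "An equivalence test of means using two one-sided tests on data from a parallel-group design". With 120 completers per arm the test "achieves 85% power at a 5% significance level when the true difference between the means is 0.0", where "the standard deviation is 7.5, and the equivalence limits are -3.0 and 3". The accompanying table gives power 0.851, 0.950 and 0.987 for limits of 3.0, 3.5 and 4.0. The narrative names only the first.

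Section 9.6 states the primary analysis for Aim 1: a two-sample t-test to "compare mean change in each nonspecific mechanism within a noninferiority test construct", followed by "An overall, 2-sided, significance level of 0.05 will be used". EO function is one of those mechanisms. Section 9.6 mentions neither equivalence nor two one-sided tests, and it gives no direction or reference arm. The sentence on the significance level recurs word for word under Aim 2, where the test is an ordinary test of difference.

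**The concern.** A noninferiority test, taken at its word, asks whether one arm is worse than the other by more than a margin. It bounds the difference on one side and says nothing about the other. A hypothesis of near-equivalence needs both sides bounded. Section 9.6 sets the decision rule for the primary outcome, and the rule it sets cannot establish the primary hypothesis and is not the test whose power was computed. With two active treatments and neither named as reference in 9.6, the tested side is also left open.

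The significance level adds a second conflict. The 5% in section 9.2 and the 2-sided 0.05 in section 9.6 look alike, but for an equivalence test they can mean a 90% or a 95% confidence interval, and the power differs between the two.

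**Working it through.** **Inputs, all from section 9.2.** n = 120 per arm; SD = 7.5; limits ±3.0; true difference 0; level 5%. One assumption: 7.5 is the SD of the pre-post change in EO function. Section 9.2 uses it that way but labels it only as a standard deviation.

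**Common quantities.**
- SE = 7.5 × √(2/120) = 0.968
- df = 120 + 120 − 2 = 238
- critical t: 1.651 (one-sided 0.05), 1.970 (one-sided 0.025)

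**Step 1: reproduce the plan's figure.** TOST passes when |observed difference| + t × (estimated SE) < limit. The exact power integrates this probability over the sampling distribution of the pooled SD. With each side at 0.05:

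| Limits | Recomputed | Section 9.2 |
|---|---|---|
| ±3.0 | 0.851 | 0.851 |
| ±3.5 | 0.950 | 0.950 |
| ±4.0 | 0.987 | 0.987 |

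Normal-approximation check for ±3.0: 2 × Φ(3.0/0.968 − 1.645) − 1 = 0.854. So the power in 9.2 is for a 90% confidence interval lying inside the limits.

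**Step 2: the same limits with a 95% interval.** With each side at 0.025 and limits ±3.0, power is 0.740. Reaching 85% would need 146 per arm, or 292/0.84 ≈ 348 enrolled at the protocol's 16% dropout.

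**Step 3: section 9.6 read literally.** One-sided noninferiority, margin 3.0, true difference 0, from the noncentral t with noncentrality 3.0/0.968 = 3.098:
- one-sided 0.05: power 0.926
- one-sided 0.025: power 0.870

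Both exceed 0.851, so the literal reading costs no power. The 0.870 is close to 0.851 only by coincidence, because section 9.2 names the two-limit test and that matches to three decimals.

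**Step 4: where the two rules disagree.** At SD 7.5 the 90% interval has half-width 1.651 × 0.968 = 1.60, so TOST fails once the observed difference exceeds 3.0 − 1.60 = 1.40 in either direction. A noninferiority test ignores one of those directions.

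| True difference, untested direction | Noninferiority passes | TOST (0.05 per side) passes |
|---|---|---|
| 0, one-sided 0.05 | 92.6% | 85.1% |
| 0, one-sided 0.025 | 87.0% | 85.1% |
| 3.0 (limit of equivalence), either level | > 99.9% | 5.0% |
| 5.0, either level | > 99.9% | about 0.01% |

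At a true difference of 0, noninferiority passes while TOST fails in 7.4% of trials, at either noninferiority level. At one-sided 0.05 this is 0.926 − 0.851, which is 0.074 before rounding. Those trials are missed equivalences rather than wrong claims. The harm lies in the last two rows, where the arms are not equivalent and the literal rule almost always passes.

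**The case against.** The strongest reply is that noninferiority is loose wording. The hypothesis, the expectation of near-equivalent effects in section 9.2 and its two symmetric limits all point to an equivalence test. The phrase in 9.6 is the outlier. Because 9.6 names no reference arm and adds that the level is 2-sided, it can be read as noninferiority in both directions, which is equivalence. The margin can be taken from 9.2, and further detail belongs in a statistical analysis plan. On that reading nothing changes in sample size, data or intended conclusion, and the issue is one of wording.

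Much of this is right. TOST is the likeliest intention, the 85% then stands, and the absence of a margin from 9.6 is not a defect in itself. What remains is that 9.6 names a different test from 9.2 for the primary outcome. An analysis plan that adopts TOST departs from 9.6, and one that follows 9.6 departs from 9.2 and from the hypothesis. The both-directions reading also leaves the level unsettled: a 90% interval gives 85% power and a 95% interval gives 74%.

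A further fair point is that 9.2 tabulates three pairs of limits. Only ±3.0 is carried into the text, so it is the best-supported choice, but the sponsor should confirm it.

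**Conclusion.** The concern holds and must be fixed, because it affects the decision rule for the primary outcome. As written, a pass under section 9.6 would not support near-equivalence: at a true difference of 3.0 in the untested direction it would occur in more than 99.9% of trials, against 5.0% for the test in section 9.2. The power figure itself is correct for its inputs and is unaffected if 9.6 is brought into line with 9.2. It falls to 74% only if a 95% interval inside ±3.0 is intended. These figures rest on the protocol's own inputs and on 7.5 being the SD of the EO change score.

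**What to change.** In section 9.6, Aim 1, replace the noninferiority and 2-sided wording for EO function with:

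> Equivalence is concluded if the 90% confidence interval for the MT − SMT difference in mean pre-post change in EO function lies within −3.0 to +3.0 (two one-sided tests, each at 0.05).

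The sponsor should confirm ±3.0 as the analysis limits. This costs one sentence for the primary outcome: 240 completers, 286 enrolled, data collection and the 85% power are unchanged. If the sponsor wants a 95% interval to govern, keep 2-sided 0.05, state that interval as the equivalence criterion, and restate the Aim 1 power in 9.2 as 74%.

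The same sentence in 9.6 covers the other nonspecific mechanisms, for which section 1.2 also hypothesises near-equivalence. Drop the noninferiority label there too. Do not carry over the EO limits, which are on the EO scale; the limits for those measures can be left to the statistical analysis plan. When rewording, note also that a pre-post comparison cannot be applied to the working alliance, which the schedule in section 6.1 places only at sessions 3 and 6 and of which Aim 4 says "given that the working alliance and subject expectations for benefit will be assessed only at 3- and 6-weeks".

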9.3 Definition of Populations

The ITT (intent to treat) sample will be all subjects who complete baseline measures. The “per protocol” sample (i.e., “treatment completers”) will be those subjects who complete at least 6 of the 8 treatment sessions.

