Candidate covariance structures will be assessed using the data's correlation structure and Akaike's Information Criterion (AIC). Random coefficients (e.g. random intercept and/or random slope) will be included in the model if they significantly improve the model fit as determined by the likelihood ratio test. Standardized residuals and Cook's distance will be used to assess the influence of outliers and individual observations. Residual plots will be used to check the multivariate normal distribution assumption. The pattern of missing data will be examined to determine its

missing mechanism and the amount. If data are missing not at random (MNAR), data imputations may be used. If other deviations from the model assumptions are detected, appropriate measures will be taken to prevent inferential bias, e.g. data transformations and use of bootstrap techniques to compute standard errors.

Potential covariates (site, age, and any baseline variables found to be significantly different ($p < .20$) between treatment groups) will be considered for model inclusion using a model selection method called least absolute shrinkage and selection operator (LASSO) (Tibshirani, 2011). This method identifies groups of covariates to form a parsimonious model; it avoids problems in stepwise procedures such as collinearity, bias, and variance deflation (Flom & Cassell, 2007); the method has recently been extended to mixed effects models (Bondell, Krishna, & Ghosh, 2010; Fan & Li, 2012; Fernandez, 2007).

Aim 3: To test the relative predictive validity of non-specific and specific mechanisms.

To test to what degree changes in non-specific and specific mechanisms predict changes in pain, mood and function, and whether these relationships depend on the treatment received, we will first test Mechanism x Treatment interactions to determine whether changes in any of the candidate mechanisms predict outcomes to a greater degree in one treatment over the other. Linear mixed effects regression models will be conducted to test, for example, a non-specific mechanism change score x Treatment interaction for each outcome change. If significant differences are observed, then the interaction effects will be interpreted to provide the unique effect of mechanism change for each treatment group.

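### Section 9.6 ties imputation to finding MNAR in the observed data, which cannot be done, and leaves the primary t-test on EO change a completer analysis under an ITT label

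*Protocol*

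**What the plan says.** Section 9.6 gives the same missing-data rule under Aim 1 and Aim 2. It has a diagnostic step, "The pattern of missing data will be examined to determine its missing mechanism and the amount", followed by an action, "If data are missing not at random (MNAR), data imputations may be used". No other circumstance for imputation is mentioned and no imputation method is named. The rule sits in the paragraph on mixed-model diagnostics.

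On the analysis itself, section 9.6 says "Primary analyses will be conducted on an ITT basis", and section 9.3 defines that set: "The ITT (intent to treat) sample will be all subjects who complete baseline measures". For Aim 1, "The primary analyses will employ the two-sample t-test to compare mean change in each nonspecific mechanism within a noninferiority test construct". The mixed model comes second: "Linear mixed models will be used as a supplemental analysis, allowing us to utilize all data collected".

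Other relevant text:

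- Section 9.2 bases the equivalence power on 120 completers per arm, and the Précis and section 9.1 expect 16% dropout from 286 enrolled.
- Section 6.2.2 defines EO function as a contrast between placebo and naloxone laboratory sessions. Section 9.6 (Aim 4) notes that it is measured only before and after treatment.
- Section 8 discontinues participants whose pain and mood worsen beyond a set percentage of baseline. It also promises efforts to obtain follow-up from those who do not complete.

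**The concern.** The rule starts from a finding the analyst cannot make. MNAR means that missingness depends on the unseen values after conditioning on the seen ones. The observed pattern can argue against data missing completely at random, but it cannot distinguish MAR from MNAR. A rule that acts on MNAR having been found therefore gives no usable instruction.

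This matters because of the primary test. A t-test on pre-post change needs a change score, so a participant with no post-treatment EO value drops out of it. Such a participant is still in the ITT set as defined. Without imputation, the primary analysis is a completer analysis. It is unbiased only if, within each arm, missingness is unrelated to EO change, or if the effects cancel between arms. MAR given other recorded data is not enough.

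The hypothesis for the primary mechanism outcome is near-equivalence. If the loss of participants makes the arms look more alike than they are, the error favours the claim.

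**Working it through.** **1. Reproduce the planning figures (section 9.2).** Inputs: 120 per arm, SD 7.5, limits ±3.0, true difference 0, each one-sided test at 0.05.

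- SE = 7.5 × √(2/120) = 0.968.
- The critical t on 238 df is about 1.651, so equivalence is declared when the absolute observed difference is at most 3.0 − 1.651 × 0.968 = 1.40.
- Exact power is 0.8515 (stated 0.851). The ±3.5 and ±4.0 rows give 0.950 and 0.987, as stated.
- Enrolment: 240 / (1 − 0.16) = 285.7, rounded up to 286.

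The planning figures are right, and they describe completers.

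**2. Who enters the primary test.** If all 286 complete baseline, the ITT set is 286 while the test is powered on 240. On the planning figures, 286 − 240 = 46 people belong to the ITT set without a change score.

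**3. Whether the trigger can be used.** For a given fit to the observed data, both MAR and MNAR explanations remain open, because they differ only in what they say about the unseen values. Examining the pattern cannot settle which holds.

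**4. Possible bias.** Let π be the proportion missing in an arm, and d the mean EO change of the missing minus that of the observed.

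Full-set difference = completers' difference + π(MT) × d(MT) − π(SMT) × d(SMT).

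The documents give no value for d, so the departures below are assumptions. They are placed in one arm, in the direction that makes completers look more alike, with π = 0.16 and the SE held at 0.968. The last two columns take a true full-set difference of 3.0, the edge of the limits.

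| Assumed departure in one arm | Shift = 0.16 × d | Share of 3.0 limit | Completers' difference | Chance of declaring equivalence |
|---|---|---|---|---|
| 0 | 0 | 0% | 3.0 | 5% |
| 0.5 SD (3.75) | 0.6 | 20% | 2.4 | 15% |
| 1.0 SD (7.5) | 1.2 | 40% | 1.8 | 34% |
| 1.5 SD (11.25) | 1.8 | 60% | 1.2 | 58% |

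Check on the second row: Φ((1.40 − 2.4)/0.968) = Φ(−1.03), about 0.15. Third row: Φ((1.40 − 1.8)/0.968) = Φ(−0.41), about 0.34.

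**5. When there is no bias, or less.** With equal π and the same d in both arms, the two terms cancel and the bias is 0. With assumed unequal dropout of 20% and 12% and the same 1 SD departure in both arms, the shift is 0.08 × 7.5 = 0.6.

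**6. Tipping point at an observed difference of 0.** Equivalence is lost when 0.16 × d exceeds 1.40, that is when d exceeds 8.76 points, or 8.76 / 7.5 = 1.17 SD in one arm.

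**The case against.** The best defence is context. The sentence belongs to the mixed-model diagnostics. A likelihood-based mixed model needs no imputation under MAR, so keeping imputation for something beyond MAR is a coherent order. That stands for the mixed model. It does not help the primary t-test, because the mixed model is supplemental.

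A reader might infer several stronger things that the text does not support:

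- **That imputation is barred unless data are MNAR, or that the rule is simply backwards.** The wording is permissive, and MNAR is only the one trigger named. Delta-adjusted and pattern-mixture methods are also imputations, so the protocol cannot be said to have chosen a MAR method for an MNAR problem. It has chosen no method.
- **That the equivalence claim will go untested against informative dropout.** A statistical analysis plan, not shown here, may add sensitivity analyses. It would still have to replace the diagnostic trigger.
- **That the discontinuation rule shows MNAR.** Pain and mood are recorded weekly (sections 6.1 and 6.2.4), so loss driven by recorded worsening points more to MAR given those data. This is a reason to condition on them, which a t-test on change does not do.
- **That 15% or 34% is the trial's error rate.** These figures assume a departure in one arm, a helpful sign and a true difference exactly at the limit, whereas section 9.2 plans on 0. The 16% is stated for completing follow-up, not for missing EO values.

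Section 8's commitment to pursue follow-up could reduce the loss. It does not say whether it reaches the post-treatment laboratory sessions, and it does not make the trigger usable.

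**Conclusion.** The point holds in this form. Section 9.6 plans, in both Aims, to read the mechanism from the observed pattern and names MNAR as the only trigger for possible imputation. That trigger cannot be applied, and no MNAR-specific method is named. Meanwhile the primary test of EO change would in practice analyse completers under an ITT label, and discontinuation depends partly on recorded worsening.

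The defect in the rule is certain, but its effect on the result is not. The effect depends on how missingness and departure differ between arms, which the documents do not give. It could be zero. With an observed difference of 0, overturning equivalence would take a departure of about 1.17 SD in one arm. The illustration assumes 16% missing EO values, the ±3 limits and SD of section 9.2, and that section's two one-sided tests at 5%, equivalent to a 90% CI. The correction should be made because the rule governs the primary mechanism outcome and is cheap to replace.

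**What to change.** Replace the rule under both Aim 1 and Aim 2 in section 9.6, and carry the change into the analysis plan before arm-level data are seen.

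1. Delete the step that determines the mechanism from the pattern and the MNAR trigger. Keep a description of the amount, timing and reasons for missingness by arm.
2. Make a MAR-based estimate for all participants in the section 9.3 ITT set the default. One option is multiple imputation using arm, baseline values and the weekly pain, mood and mechanism data, followed by the planned comparison of change. The mixed model as written, with only time, arm and their interaction, does not draw on the weekly data for EO. Report the completer t-test as a supporting analysis.
3. For EO change, add a pre-set delta-adjusted sensitivity analysis. Shift the imputed changes separately in each arm over a stated range, and report the shifts at which the 90% CI for the difference leaves ±3.

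This needs new wording and modest extra programming, and no new data. The drawback for the sponsor is that the equivalence claim may prove less robust than the completer test suggests.
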